10.1. Patient-reported Outcomes Measurement Information System (PROMIS)–Cognitive Function

The PROMIS Item Bank v2.0–Cognitive Function is a self-administered questionnaire that assesses multiple aspects of mental fatigue and cognitive function in the past 7 days prior to the administration of the questionnaire. (2) It uses a Likert-type rating scale (eg, "5=Never" to "1=Very often"). A total raw score ranging from 0 to 160 scores is calculated by summing participants' responses to each item. Higher scores represent better cognitive function. All questions must be answered in order to calculate total scores.

Descriptive statistics for observed values and changes from baseline in total PROMIS score will be summarized for each domain of the questionnaires for participants in the Safety population at each scheduled visit in 3.

Listings of the PROMIS data will be provided for participants in the Safety population and participants will be flagged to denote PD Evaluable population, if applicable.

10.2. Patient Global Impression of Change (PGIC)

The Patient Global Impression of Change (PGIC) is a single-item questionnaire that assesses the participant's perception of change in his/her overall health status since the start of the study using a Likert-type rating scale (e.g., "Very much improved" to "Very much worse").

The number and percentage of participants in each level of PGIC will be summarized by participant in Safety population at end of treatment visit.

Descriptive statistics for observed values will be summarized for participants in the Safety population at end of treatment.

Listings of the PGIC data will be provided for participants in the Safety population and participants will be flagged to denote PD Evaluable population, if applicable.

10.3. Modified Fatigue Impact Scale (MFIS)

The MFIS is a self-administered questionnaire that assesses the impact of fatigue. (3) Participants respond using a likert-type rating scale (e.g., "Never" to "Almost always"). Items on the MFIS can be aggregated into three subscales (physical, cognitive, and psychosocial), as well as into a total MFIS score. All items are scaled so that higher scores indicate a greater impact of fatigue on a person's activities.

The MFIS questions yields 3 subscales and one total score:

- Physical

This scale can range from 0 to 36. It is computed by adding raw scores on the following items: 4+6+7+10+13+14+17+20+21. If more than 4 items are missing, then the scale score will be missing. Otherwise the scale score will be imputed by multiplying 9 by the average score of the rest of non-missing items. For example, if one item is missing, the scale score will be derived as the total score of rest of non-missing 8 items divided by 8 and multiplied by 9.

- Cognitive

This scale can range from 0 to 40. It is computed by adding raw scores on the following items: 1+2+3+5+11+12+15+16+18+19. If more than 5 items are missing, then the scale score will be missing. Otherwise the scale score will be imputed by multiplying 10 by the average score of the rest of non-missing items. For example, if one item is missing, the scale score will be derived as the total score of rest of non-missing 9 items divided by 9 and multiplied by 10.

- Psychosocial

This scale can range from 0 to 8. It is computed by adding raw scores on the following items: 8+9. If one item is missing, the scale score will be imputed by multiplying 2 by the non-missing item. If more than one item is missing, then the scale score will be missing.

- Total MFIS

The total MFIS score can range from 0 to 84. It is computed by adding scores on the physical, cognitive, and psychosocial subscales. If any subscale is missing, the total score will be missing.

Descriptive statistics for observed values and changes from baseline will be summarized for MFIS total scores and each subscale for participants in the Safety population at each scheduled visit in 3.

Listings of the MFIS data will be provided for participants in the Safety population and participants will be flagged to denote PD Evaluable population, if applicable.

11. Pharmacokinetics

PK samples (Plasma and CSF) will be collected as scheduled in **Table 3**. The actual date and time (24h clock time) of each sample collection will be recorded in the source documents and eCRF.

The lower limit of quantification (LLOQ) for IW-6463 is 1.0 ng/mL. Plasma and CSF concentrations below the limit (BLQ) of quantification will be assigned a value of $\frac{1}{2}$ LLOQ for the calculation of summary statistics and will be presented as BLQ in the listing.

Descriptive statistics for plasma and CSF concentrations of IW-6463 will be summarized for participants in PK Evaluable population at each scheduled assessed timepoint in **Table**

3. The calculation and summary of PK parameters may be described and reported outside of this SAP.

Listings of the plasma and CSF concentrations of IW-6463 data will be provided for participants in the PK Evaluable population.

A population PK approach based on sparse PK data will be used to determine exposure and oral clearance of IW-6463. If data allow, influence of participant demographics (eg, age, race) and effects of concomitant medications on IW-6463 PK exposure will be evaluated. In addition, exposure-effect relationships (such as hemodynamic, biomarkers, and safety parameters) may also be explored. PK parameters of interest include but are not limited to the area under the concentration-time curve from time zero (predose) to 24 hours postdose (AU_{C_{tau}}), time to C_{max} (T_{max}), t_{1/2}, maximum observed plasma concentration (C_{max}), plasma concentration observed at the end of a dosing interval (C_{trough}), apparent total plasma clearance (CL/F), apparent volume of distribution (Vz/F), and CSF:plasma concentration ratio, and will be calculated and presented as data permit.

These analyses will be performed outside of the SAP and reported separately outside of the clinical study report.

12. Pharmacodynamics

Descriptive statistics for plasma biomarkers and imaging endpoints from MRS and ASL at each assessment time point and the change from baseline at each post-baseline time point will be summarized for participants in the Safety and PD Evaluable population (if applicable). Of the imaging endpoints from fMRI, only the fractional amplitude of low-frequency fluctuations in the different networks at each assessment timepoint and the respective change from baseline at each post-baseline time point will be summarized. Assessment of the change from baseline in fMRI-blood-oxygen-level-dependent (BOLD) signals with a visual stimulus, will be described and conducted outside of this SAP and reported separately.

Listings will be provided for all participants in Safety population.

13. Immunogenicity

Immunogenicity testing will not be conducted in this study.

14. Changes in the Planned Analysis

The following changes/clarifications will be made to the analyses described in the study protocol.

- Updated to present all the protocol deviations instead of Major protocol deviations in a data listing.
- Removed Shift tables for QTcF interval increases category: >30 ms, but ≤ 60 ms, and QTcF interval increases by >60 ms.
- Added clarification for definition of a PD Evaluable Population (Section 4.3) only if the full planned number of participants enrolled in the study.
- Added that the assessment of the change from baseline in fMRI-blood-oxygen-level-dependent (BOLD) signals with a visual stimulus (Section 12) will be described and conducted outside of this SAP and reported separately.
- Analyses of the clinical outcomes assessments/participant questionnaire data in Section 10 was revised to be conducted on the safety population instead of the PD Evaluable population
- Medical History is analyzed by SOC and PT
- Blood pressure (supine and standing) will be described by each value and change from baseline
- Potentially clinically important (PCI) criteria will also be assessed for Standing and Orthostatic Criteria

15. References

1. Posner K 2007. Suicidality issues in clinical trials: Columbia suicidal adverse event identification in FDA safety analyses. Division of Metabolism and Endocrinology Products Advisory Committee Meeting, Food and Drug Administration.
2. www.healthmeasures.net/images/PROMIS/manuals/PROMIS_Cognitive_Function_Scoring_Manual.pdf.

16.1. Schedule of Study Procedures

Table 3: Schedule of Events

Study Period →	Screening	Treatment Period (assessments are predose unless noted)						F/U
		In-clinic Screening	In-clinic Visit	At-home Visit ¹	At-home Visit ¹	In-clinic EOT Visit ²		
Visit Type/Name →	In-clinic Screening	Day 1	Day 8 (±2 days)	Day 15 (±2 days)	Day 29 (-4 days)		Day 43 (±4 days)	
					Pre	2 h	4 h	6 h
Visit Day (window) →	Day -28 (-28 to -10 days)				(-30 m)			
Study Procedure ↓								
ICF signed	X							
Eligibility evaluation	X	X						
Demographics	X							
Drug/alcohol screen ²	X							
Medical history	X	X						
Physical examination ³	X	X	X	X	X			X
Weight (W), height (H)	W, H	W		W	W			W
12-lead ECG ⁴	X	X			X			X
ECHO ⁵	X							
BP (including orthostatic) & pulse ⁶	X	X	X	X	X		X	X
Oral temp, O ₂ , & RR	X	X	X	X	X		X	X
Clinical safety samples ⁷ (chemistry, coag/hematology, UA)	X	X ⁸	X	X	X			X
Pregnancy test ⁹	X	X	X	X	X			X
C-SSRS		At each scheduled and unscheduled visit						
Study drug supply/accountability/return ¹⁰		X	X	X	X			
Participant diary	Issued at Screening; reviewed at each scheduled visit; collected at Follow-up							

Study Period →	Screening	Treatment Period (assessments are predose unless noted)					F/U						
		In-clinic Screening	In-clinic Visit	At-home Visit ¹	At-home Visit ¹	In-clinic EOT Visit ²							
Visit Day (window) → Study Procedure ↓	Day -28 (-28 to -10 days)	Day 1	Day 8 (±2 days)	Day 15 (±2 days)	Day 29 (-4 days)		Day 43 (±4 days)						
					Pre	2 h	4 h	6 h					
					(±30 m)								
Study drug dosing ^{10,11}		QD Days 2–28, including at home, at a consistent time (±1 h of Day 1 dose time)		In clinic									
AE/SAE evaluation	From Screening through Follow-up												
Prior/concom. med. rev.	From Screening through Follow-up												
Blood sample for PK			X	X	X	X	X						
CSF sample for PK							X						
Blood sample for PD biomarkers ⁷	X	X		X	X		X						
Neuroimaging ¹²	X	X				X							
MFIS		X			X								
PGIC					X								
PROMIS–Cognitive function		X			X								
Visit discharge ¹³		~4h post											
Study completion							X						

AE=adverse event; BP=blood pressure; coag=coagulation; concom=concomitant; CSF=cerebral spinal fluid; C-SSRS=Columbia Suicide Severity Rating Scale; ECG=electrocardiogram; ECHO=echocardiogram; EOT=end of treatment; F/U=follow-up; h=hour(s); H=height; ICF=informed consent form; m=minute(s); med=medication(s); MFIS=Modified Fatigue Impact Scale; O₂=oxygen saturation; PD=pharmacodynamic; PGIC=Patient Global Impression of Change; PK=pharmacokinetic(s); post=postdose; Pre=predose; PROMIS=Patient-Reported Outcomes Measurement Information System; QD=once daily; rev=review; RR=respiratory rate; SAE=serious adverse event; UA=urinalysis; VS=vital signs; W=weight

¹Visit will be conducted within the allowable timeframe, either at the participant's home or in the Study Center per participant/Study Center preference. If the Follow-up Visit is conducted at home: The investigator will perform a medical review of the safety assessments conducted during the at-home F/U visit and may contact the participant via telephone if further follow-up is needed.

² All participants will be asked to return to the Study Center for the EOT visits.

For premature study drug discontinuations: If possible, participants who prematurely discontinue study drug will be asked to complete the EOT assessments prior to departure and then complete the Follow up Visit as scheduled

² See Protocol Section **Error! Reference source not found.** for a list of drugs to be screened.

³ A complete physical exam will be done at Screening and Follow-up; a symptom-directed exam can be performed at all other visits.

- 4 ECGs will be performed after the participant has been resting supine for ≥ 5 minutes and should be obtained before blood draws (or ≥ 10 m after a blood draw, if necessary). See Protocol Section **Error! Reference source not found.** for details. When timing coincides, ECGs and vital signs can be assessed together.
- 5 Screening ECHO is necessary only in the absence of a documented ECHO performed within 3 months of Day 1
- 6 All BP and pulse measurements will be obtained with an automated BP device (left arm preferred) prior to blood draws (or ≥ 10 m after a blood draw, if necessary). Manual readings are allowed only if automatic is not available.
--*Supine BP at Screening (only)*: Record the average of 2 measurements obtained at 2-minute intervals after the participant has rested quietly in a semi-recumbent/supine position for ≥ 5 minutes
--*Orthostatic vital signs (all scheduled visits)*: Participant must rest quietly in a supine/semi-recumbent position for ≥ 5 minutes before supine measurements are recorded, then assume sitting position for ≥ 1 minute, and finally assume standing position for 2 (± 1) minute before standing measurements are recorded. Results will be used to calculate and record orthostatic BP and pulse.
- 7 Although IW-6463 can be taken with or without food, participants are requested to fast for 3 to 4 hours prior to all clinical safety and PD laboratory sample collections. Water and a light snack (if previously approved), are allowed upon awakening on the morning of the visit. **For in-clinic visits**, because participants may be vulnerable to metabolic decompensation during any catabolic state, a standardized meal with a low glycemic index will be administered just prior to the start of this fasting period. **For at-home visits**, participants will either be counseled on what to consume prior to the fasting period, or will be given a standardized meal by home health services. For details regarding standardized snacks and meals, see the Nutrition Guidelines for this study.
- 8 Safety laboratory results must be assessed for clinical significance prior to initiation of study drug dosing on Day 1; local laboratory results can be used for the Day 1 eligibility assessments; a second set of samples must also be sent to the Central laboratory.
- 9 For women of reproductive potential (defined in Protocol Section **Error! Reference source not found.**), a serum pregnancy test will be conducted at Screening and at the Follow-up Visit; urine-based pregnancy tests will be acceptable at all other scheduled visits (unless serum testing is required by local regulation or the institutional review board/independent ethics committee [IRB/IEC]). A reviewed and documented negative result is required at Screening and again prior to study drug initiation on Day 1. A confirmed positive result at any time during the study will result in immediate discontinuation of study drug. See Protocol Section **Error! Reference source not found.**
- 10 Study drug supply will be distributed on Day 1 and will be resupplied as applicable. Dosing compliance (via tablet count) will be recorded at each scheduled visit during the Treatment Period. Participant diaries will also be checked at each visit for completeness. Participants will be instructed to bring in any unused study drug supply and their diary to each scheduled visit through EOT.
- 11 Participants will be instructed to take their study drug dose on Days 2 through 28 at a consistent time each day, corresponding to the Day 1 dose administration time (± 1 h). *Exception>Note:* For the Days 8, 15, and 29/EOT visits, they will take their dose during the visit to allow for appropriate timing of pre- and postdose assessments. Attempts should be made to schedule the Day 8 and 15 visits (at home or in clinic) such that dosing can still occur at approximately the same time as the Day 1 and subsequent doses.
- 12 Includes magnetic resonance spectroscopy (MRS); arterial spin labeling (ASL), and functional magnetic resonance imaging blood-oxygen-level-dependent (fMRI-BOLD) imaging. Scanners that lack fMRI capabilities may be considered for use in this study with Sponsor approval. See Protocol Section **Error! Reference source not found.** and the study's scanning guidelines document for details.
- 13 Participants will be observed for ≥ 4 hours postdose and thereafter may be released from the study center per Investigator discretion

16.2. Missing Date Information for Adverse Events

The following imputation rules apply to cases in which the start date is incomplete (i.e., partial missing) for adverse events.

Missing day and month

- If the year is the same as the year of the date of the first dose of double-blind study drug, then the day and month of the date of the first dose of double-blind study drug will be assigned to the missing fields.
- If the year is prior to the year of the date of the first dose of double-blind study drug, then December 31 will be assigned to the missing fields.
- If the year is after the year of the date of the first dose of double-blind study drug, then January 1 will be assigned to the missing fields.

Missing month only

- The day will be treated as missing and both month and day will be replaced according to the above procedure.

Missing day only

- If the month and year are the same as the month and year of the date of the first dose of double-blind study drug, then the date of the first dose of double-blind study drug will be assigned to the missing day.
- If either the year is before the year of the date of the first dose of double-blind study drug or if both years are the same but the month is before the month of the date of the first dose of double-blind study drug, then the last day of the month will be assigned to the missing day.
- If either the year is after the year of the date of the first dose of double-blind study drug or if both years are the same but the month is after the month of the date of the first dose of double-blind study drug, then the first day of the month will be assigned to the missing day.

If the stop date is complete and the imputed start date as above is after the stop date, the start date will be imputed by the stop date.

If the start date is completely missing and the stop date is complete, then the following algorithm is used to impute the start date:

- If the stop date is after the date of the first dose of double-blind study drug, the date of the first dose of double-blind study drug will be assigned to the missing start date.
- If the stop date is before the date of the first dose of double-blind study drug, the stop date will be assigned to the missing start date.

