9.1. Adverse Events

Adverse events will be coded using MedDRA Version 24.0.

Pretreatment AEs are defined as AEs with a start date between the informed consent date and the date of the first dose of study drug.

Treatment-emergent AEs are defined as AEs reported in the clinical database with a start date on or after the first dose of study drug until the end of the follow-up period.

An overall summary of the number of participants in the Safety population with AEs will be presented, including the number and percentage of participants with AEs, pretreatment AEs, TEAEs, severe TEAEs, drug-related TEAEs, serious AEs, AEs leading to death, TEAEs leading to study drug discontinuation and Treatment-emergent adverse events of special interest (AESIs).

All AEs will be presented in listings for the Safety population, and AEs will be flagged to denote pretreatment AEs and TEAEs. Incomplete AE start dates will be imputed as described in Section 16.2.

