16.3. Missing Date Information for Prior or Concomitant Medications

For prior or concomitant medications, incomplete (i.e., partially missing) start date and/or stop date will be imputed. When the start date and the stop date are both incomplete for a patient, impute the start date first.

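### SAP 16.2 checks an imputed AE start only against a complete stop date, so an event whose recorded stop month precedes the first-dose month can be classed as a TEAE

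*SAP*

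**What the plan says.** SAP 16.2 handles incomplete AE start dates. Where day and month are both missing, the branch "If the year is the same as the year of the date of the first dose of double-blind study drug" applies, and "then the day and month of the date of the first dose of double-blind study drug will be assigned to the missing fields". Where only the month is missing, "The day will be treated as missing and both month and day will be replaced according to the above procedure", so the result is the same. The study is open label; I read the references to double-blind drug in that section as meaning IW-6463.

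One sentence then protects against an impossible order of dates. Its condition is "If the stop date is complete and the imputed start date as above is after the stop date"; when that is met, the recorded stop replaces the imputed start. A completely missing start carries the same condition: "If the start date is completely missing and the stop date is complete, then the following algorithm is used to impute the start date".

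No rule imputes or uses a partial AE stop date. SAP 16.3.2 deals with incomplete stop dates, but its parent section is limited to medications: "For prior or concomitant medications, incomplete (i.e., partially missing) start date and/or stop date will be imputed".

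SAP 9.1 sends incomplete AE starts to Section 16.2 and classifies by date alone: "Treatment-emergent AEs are defined as AEs reported in the clinical database with a start date on or after the first dose of study drug", through the end of follow-up. Protocol 9.3.8 and 10.2.1.1 define a TEAE by substance instead: the event must be absent before treatment and emerge during it, or worsen from its pretreatment state.

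**The concern.** Imputing toward treatment-emergent is sound when onset could fall on either side of the first dose. Here it could not. If an event ended in a calendar month before the month of first dose, the record excludes onset on or after dosing, even without a stop day. The rule ignores that information and produces a start later than the recorded end. The event meets neither limb of the protocol's TEAE definition.

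The SAP evidently intends recorded stop information to override the imputation, since it does so for complete stop dates. Two records that both prove the event pretreatment are therefore classed differently, depending only on whether the stop day was entered.

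At stake is the split between the pretreatment and TEAE tables (SAP 9.1.2 and 9.1.3), through which the incidence and severity of AEs, one of the two primary endpoints, is reported. The error runs one way, into the TEAE tables. Two later imputations can add to it. Under SAP 9.1.3 a missing severity becomes Mild for a pretreatment AE but Severe for a TEAE. Under SAP 9.1.4 a missing causality becomes Related for a TEAE.

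**Working it through.** The plan has no figure of its own to reproduce here; the check applies the written rule to test records.

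**Inputs.** The start and stop rules are from SAP 16.2 and the TEAE rule from SAP 9.1. AE collection begins at consent (protocol 4.1.1). Screening lasts at most 28 days (protocol 4.6), and its procedures are completed 10 to 28 days before dosing (protocol 4.1.1). A maximum of 20 participants is treated (SAP 4.1). The first-dose date of 10 Sep 2021 is assumed for illustration.

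**Rule applied literally, then with the stop check extended to month-and-year stops:**

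| Recorded start | Recorded stop | Imputed start, SAP 16.2 | Class | With extended check |
|---|---|---|---|---|
| 2021 | Aug 2021 | 10 Sep 2021 | TEAE | 31 Aug 2021, pretreatment |
| day 15, month unknown, 2021 | Aug 2021 | 10 Sep 2021 | TEAE | 31 Aug 2021, pretreatment |
| 2021 | 25 Aug 2021 | 25 Aug 2021 | pretreatment | unchanged |
| Aug 2021 | Aug 2021 | 31 Aug 2021 | pretreatment | unchanged |
| 2021 | Sep 2021 | 10 Sep 2021 | TEAE | unchanged |
| 2021 | 2021 | 10 Sep 2021 | TEAE | unchanged |

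Only the first two rows are wrong: the latest possible stop, 31 Aug, precedes the first dose on 10 Sep, yet the imputed start is 10 Sep. The third row shows the existing check working once a stop day is present. In the last two rows the timing is ambiguous, and TEAE is the reasonable default.

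**Can it arise?** Twenty-eight days before 10 Sep is 13 Aug, so an event can begin after consent and end in August. Over the 365 possible first-dose dates of 2021, the date 10 days earlier falls in an earlier month of the same year for 110 (110/365 = 30%). The date 28 days earlier does so for 308 (308/365 = 84%). These shares show only that the calendar allows the case. They are not an estimate of how often it occurs.

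**Size.** SAP 9.1.2 counts a participant once per row. One added participant with no other TEAE in that row changes it by 1/20 = 5.0 percentage points with 20 in the Safety Population. If the participant already has a TEAE there, the row does not change.

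**The case against.** The strongest objection is that the record is improbable. Participants keep a daily diary from Screening with dates and times of health changes (protocol 8.4), and it is reviewed at each scheduled visit. Investigators report onset and resolution date and time (protocol 10.1), and missing data must be explained (protocol 11.1). Moreover, a window of at most 28 days touches at most two calendar months. If an event began after consent and ended in a month before the first-dose month, it began in that same month. A site that worked this out would enter the start month, and the missing-day rule would then classify the event correctly, as in the fourth row of the table. This stands as an argument that the case is rare. It does not make the rule right, since SAP 16.2 exists for records that fall short of what was asked.

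It can also be said that the error only over-counts TEAEs, and that all AEs are listed and flagged, so an impossible date order could be spotted in a study this small. That is true, but it relies on someone noticing and overriding a pre-specified rule.

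Three stronger readings are tempting and lack support:

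- A reader might infer that the primary endpoint itself is miscounted. The endpoint is incidence and severity of AEs, not of TEAEs (protocol 3, SAP 3.2.1). The event stays in the all-AE count and moves only between sub-tables. The other primary endpoint should not be touched: an event that ended before dosing should carry no dose reduction or withdrawal.
- A reader might divide by 12 and quote a larger shift. Twelve is the target for evaluable participants; about 20 are expected in the Safety Population (protocol 4.3).
- A reader might turn calendar shares such as those above into an error rate. They are conditional on a record with both dates partial, and the documents do not say how many such records there are.

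**Conclusion.** The point holds, and it is minor. As written, SAP 16.2 with SAP 9.1 returns a provably wrong class for one narrow kind of record: start month missing, start year equal to the dosing year, and stop known to a month and year earlier than the first-dose month. This is a stated rule giving a wrong answer, not a missing branch. The result does not depend on the assumed first-dose date, only on the order of the months.

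The number affected is unknown and probably very small, possibly none. The 5-point shift assumes 20 in the Safety Population and no other TEAE for that participant in the row. Assignment of Severe or Related applies only if that field is also still missing after all efforts to obtain it.

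**What to change.** Add one sentence to SAP 16.2 after the existing stop-date check:

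> If the stop date has month and year but no day, and the imputed start date is after the last day of that month, the start date is set to the last day of that month.

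This moves only events that the record proves to have ended before dosing. Stops in the first-dose month still leave onset uncertain, and those events stay TEAEs. Extending the sentence to stops known only to the year would do nothing for this defect, because 31 December of the dosing year cannot precede a first dose in that year.

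The cost is one sentence in the SAP and about one line of programming, with no new data collection. A completely missing start with a partial stop has no rule at all in SAP 16.2; that separate gap could be closed in the same edit.
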